The screening history may be obtained by phone. Documentation of a physical examination performed by a non-study physician within the previous 12 months may be used in lieu of an in-person physical examination; in this case, a physical examination will also be performed by a study physician at Visit 1. To obtain physical examination results performed off-site, subjects will be given an MGH "authorization for disclosure of medical information from another facility" form. If a physical examination is performed solely for the purposes of this study, study funds will pay for the cost of the physical examination. Remote screening laboratory studies will be performed at MGH on a blood sample shipped by the subject or at a local laboratory site (e.g. LabCorp,

Quest, etc.); study funds will pay for all phlebotomy and shipping costs. Laboratory studies already performed within the previous 6 months will be in lieu of repeating screening studies unless abnormal.

Cohort 1 Protocol: Gonadotropin secretion (N=10)

Subjects will complete four outpatient visits. Procedures for each visit are described below:

Screening Visit: Described above

If eligibility criteria are all met, a member of the study team will call the subject and schedule them for two visits at the Clinical Research Center.

As mentioned above, we will ask subjects being treated with dopamine agonists to complete a washout period prior to the frequent blood sampling visit(s). The washout period will last at least 4 weeks.

Visit 1

- Admission to the Clinical Research Center (CRC)
- q10 minute blood sampling (3 mL q 10 min) x 12 hours without intervention to assess endogenous LH pulsatility. All samples will be assayed for LH. Progesterone (P4) will be measured on the first sample. FSH, prolactin, and estradiol (E2) will be assayed from pools of the frequent sampling studies.^{3,4}

Visit 2 (within 22 days of Visit 1)

- Admission to the Clinical Research Center (CRC)
- q10 minute sampling (3 mL q 10 min) x 12 hours
- Administration of 10 boluses of kisspeptin 0.313 µg/kg IV every hour beginning at hour 1 of the study. All samples will be assayed for LH. Progesterone (P4) will be measured on the first sample. FSH, prolactin, and estradiol (E2) will be assayed from pools of the frequent sampling studies.^{3,4}
- Administration of one bolus of GnRH 0.075 ug/kg IV at hour 11 of the study.

Visit 3: Final follow-up study visit

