This visit will occur within a month after subjects have completed their Visit 2. The total blood drawn during this visit is 13mL. If any test result is abnormal, the subject will be followed until screening tests (CBC, BUN, creatinine, liver function studies) return to the ranges specified in eligibility criteria. If hemoglobin <10 g/dL then subjects will be provided with a one month supply of iron pills.

Cohort 2 Protocol: Folliculogenesis (N=5)

Subjects will complete 9 outpatient visits. Procedures for each visit are described below:

Screening Visit: Described above

If eligibility criteria are all met, a member of the study team will contact the subject to schedule Visit 1.

Visit 1: Day 1 of kisspeptin administration

- Participants will undergo a pelvic ultrasound to assess presence or absence of follicular growth. It is at investigator discretion to halt participation of any subject with evidence of follicular growth from the Visit 1 ultrasound.

- Participants will come to the Reproductive Endocrine Unit, or the CRC, where a study physician will initiate the administration of kisspeptin.
 - Option 1: Kisspeptin 0.313 – 13.19 µg/kg SC q60 – q240 minutes will be administered subcutaneously.
 - Option 2: Kisspeptin 0.313 µg/kg IV q 90 minutes will be administered using a closed IV system.
- Up to 10 blood samples will be drawn during the visit. One or more 3mL samples will be collected just before the initial kisspeptin is delivered and additional 3mL samples will be collected after the bolus is delivered, over the course of the next 80 minutes (maximum total blood collection volume of 30mL) to define the LH response to the kisspeptin. All blood samples will be assayed for LH. P4 will be measured on the first sample, and prolactin will be measured on both the first and final samples. Pooled samples will be used for measurements of FSH and E2. Time of day of sample collection will be recorded.
- Vital signs will be collected at least once during the visit.

Visits 2-7: Daily blood sampling (days 2-7 of kisspeptin administration)

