- The GnRH-induced gonadotropin responses to a single bolus of kisspeptin (administered via pump(s)) will be monitored with up to 10 blood samples: One or more 3mL samples will be collected just before a kisspeptin bolus is delivered and additional 3mL samples will be collected after the bolus is delivered, over the course of the next 80 minutes, to define the LH response to the kisspeptin bolus. Maximum blood volume collected each day is 30mL . Sample collection will begin at the same time of the day ± 3 hours from the time collection began at Visit 1.
- All blood samples will be assayed for LH. P4 will be measured on the first sample, and prolactin will be measured on the first and final samples. Pooled samples will be used for measurements of FSH and E2. Time of day of sample collection will be recorded.
- Pelvic ultrasounds will be performed at Visit 3 or Visit 4 to monitor follicular growth. This ultrasound is intended to ensure that the rate of follicular growth and number of follicles do not indicate hyperstimulation, which is considered extremely unlikely to occur, based on prior data of kisspeptin administration in this dose range.
- Vital signs will be collected at least once during each daily visit.

Visit 8: Final Visit (day 8 of kisspeptin administration)

- At least 30 minutes after kisspeptin administration ends, participants will undergo final hormonal measurements: LH, FSH, E2, P4, prolactin; and safety laboratory studies: AST, ALT, BUN, Cr, hemoglobin, white blood cell, platelet counts, and TSH. The total blood drawn during this visit will not exceed 20mL.
 - The study team will contact participants if any safety value is outside the desired range (as stated in eligibility criteria) and arrange appropriate follow-up as needed. If hemoglobin <10 g/dL then subjects will be provided with a one-month supply of iron pills.
- Pelvic ultrasound will be performed to assess follicular growth.

Blood Draws:

Cohort 1: The total volume of blood drawn during screening will not exceed 18ml. The progesterone and estradiol tests drawn at screening may be repeated; approximately 5mL will be drawn. The study subjects will undergo two 12 hour sampling studies on two separate days, approximately 220mL will be drawn for each study. The total volume of blood drawn for final

follow-up is approximately 13mL. The total volume of blood drawn over the course of the protocol is within PHRC guidelines and will not exceed 550 mL.

Cohort 2:

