GnRH: Long experience with GnRH has shown that a physiologic dose of GnRH is 25-75 ng/kg.⁹ To ensure that a response to GnRH is seen, the dose of GnRH 75 ng/kg IV x1 is used in these protocols. The dose used to achieve pituitary priming is GnRH 25 ng/kg SC q2h x6d, which has been shown to successfully achieve priming.¹⁰

Data suggests there is no interaction between kisspeptin administration and changes in prolactin levels in humans. Data recently published in Clinical Endocrinology show that prolactin levels are not significantly changed immediately following kisspeptin-54 injections (6.4 nmol/kg) in healthy women.¹¹ Our group has observed similar short term results after administration of single boluses of kisspeptin-10 (0.313 µg/kg; 0.24 nmol/kg) in healthy men and men with IHH. Long-term follow up data collected by our group in healthy men, cycling women, and postmenopausal women, as well as men and women with IHH, also show that prolactin levels do not significantly change after administration of boluses or infusions of kisspeptin-10.

Cohort 1 CRC Visits

Females will undergo a pregnancy test at screening and again at admission prior to receiving kisspeptin. Subjects will receive isovolumetric replacement with saline during blood sampling. Kisspeptin will be administered by a CRC RN. Vital signs (HR, BP, RR, and T) will be measured every 1-4 hours throughout the frequent sampling portions of the protocol and every 10 minutes for up to 30 minutes after kisspeptin administration.

Termination criteria will include: 1) blood pressure > 180 mmHg systolic or > 105 mmHg diastolic at any point during the protocol; 2) development or suspicion of an allergic or serious adverse reaction; 3) positive pregnancy test; 4) temperature $\geq 101.5^{\circ}\text{F}$ at any point in the study. Any subject who develops high blood pressure or an allergic reaction will receive follow-up inpatient medical care until the issue is resolved, with subsequent outpatient and/or phone follow-up as needed. The CRC is fully equipped to handle medical emergencies, with trained staff, a bag-valve mask in the room, a crash cart on the floor, and rapid access to a physician code team.

Cohort 2 daily blood sampling visits

Females will undergo a pregnancy test at screening and again prior to receiving kisspeptin. Kisspeptin will be administered via a pump(s). Vital signs (HR, BP, RR, and T) will be measured at least once during each daily blood sampling visit.

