Termination criteria will include: 1) blood pressure > 180 mmHg systolic or > 105 mmHg diastolic at any point during the protocol; 2) development or suspicion of an allergic or serious adverse reaction; 3) positive pregnancy test; 4) temperature $\geq 101.5^{\circ}\text{F}$ at any point in the study. Any subject who develops high blood pressure or an allergic reaction will receive follow-up inpatient medical care until the issue is resolved, with subsequent outpatient and/or phone follow-up as needed.

BIOSTATISTICAL ANALYSIS

Assays

Given the long-term ongoing nature of this study, the assay methodologies employed to characterize the biochemical profile (both reproductive and metabolic) will be based on standard accepted methods as established by the Reproductive Endocrine Reference Laboratory. As such these methods may include immunoassays, measurement using standard laboratory platforms, radioimmunoassays, and mass spectroscopy. We anticipate that these methods will continue to evolve as the diagnostics field changes.

Cohort 1 (Specific Aim 1)

Population Size

Each patient will serve as her own control. The primary outcome will be the number of LH pulses on the first biochemical assessment (no kisspeptin) compared to the second assessment (+kisspeptin). Many studies in the literature have reported a decreased LH pulse frequency in hyperprolactinemia with one study (using q 10 minute sampling) documenting approximately 2.25 pulses / 12 h in hyperprolactinemic individuals.¹² During the second admission, by administering 10 boluses of kisspeptin, 10 LH pulses should be observed. For the purposes of these calculations however, 8 pulses will be conservatively estimated because some of those pulses will coincide with/conceal endogenous pulses. For a difference of 8 and an SD of 6.8, 10 subjects will need to be studied before and after kisspeptin to achieve 90% power at alpha = 0.05.

Data Analysis and Interpretation

LH pulses will be identified using a modified version of the Santen and Bardin method of pulse detection which has been validated *in vivo*.^{3,4} The primary outcome will be change in the frequency of LH pulses in response to kisspeptin administration. The hypothesis will be accepted if the change in LH frequency on kisspeptin is higher during intermittent kisspeptin administration (second assessment) than in the absence of kisspeptin administration. Mean LH level and LH pulse amplitude will also be calculated and used in secondary analyses.

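### Cohort 2 Visit 1 guarantees no blood pressure or temperature reading after the first kisspeptin dose

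*Combined protocol and SAP*

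**What the plan says.** Three statements govern Cohort 2 vital signs, and all set the same floor.

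- Cohort 2 Protocol, Visit 1: "Vital signs will be collected at least once during the visit".
- Cohort 2 Protocol, Visits 2-7: "Vital signs will be collected at least once during each daily visit".
- Cohort 2 daily blood sampling visits: "Vital signs (HR, BP, RR, and T) will be measured at least once during each daily blood sampling visit".

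None gives a time relative to a bolus. The termination criteria that follow the third statement include "blood pressure > 180 mmHg systolic or > 105 mmHg diastolic at any point during the protocol" and a temperature of 101.5°F or more. The other two criteria are an allergic or serious adverse reaction and a positive pregnancy test.

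At Visit 1 a study physician starts kisspeptin. Blood is drawn before the first dose and over the 80 minutes after the bolus.

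The section on Cohort 1 CRC Visits lists the same termination criteria. It requires vital signs every 1-4 hours during frequent sampling and also "every 10 minutes for up to 30 minutes after kisspeptin administration".

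**The concern.** A stopping rule based on blood pressure or temperature works only if those readings are taken when they could matter. The first pump or closed-IV dose is an obvious time to look. For a participant who was not in Cohort 1, it is also the first kisspeptin given in this study. As written, a fully compliant Visit 1 can record blood pressure and temperature only beforehand. A change after that dose could then go unrecorded even though two termination criteria refer to it. Without a required pre-dose set, a single later reading would also lack a same-day baseline.

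What is at stake is safety documentation around one dose in five participants.

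**Working it through.** The plan gives no figure to reproduce, so the check is a reading of the text with simple counts.

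**1. Can one pre-dose set satisfy Visit 1?** Visit 1 has several steps before dosing: the pelvic ultrasound, the repeat pregnancy test, at least one blood sample and, for participants whose screening examination was done off-site, a physical examination by a study physician. The single required set could be taken at any of these. No other section requires a set after the dose at Visit 1. Guaranteed post-dose sets at Visit 1: 1 required − 1 taken pre-dose = 0.

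**2. When is the next required set?** It is at Visit 2, on day 2. The Visits 2-7 text says: "Sample collection will begin at the same time of the day ± 3 hours from the time collection began at Visit 1". Assume that Visit 2 is the next calendar day and that its set is taken near the start of sampling. The interval from the start of Visit 1 sampling is then 24 − 3 = 21 h to 24 + 3 = 27 h. This is an indicative range, not a maximum. The Visit 2 set could be taken at the end of an 80-minute sampling period, giving up to 27 h + 80 min = 28 h 20 min. The clock also starts at a pre-dose sample, so the time from the dose itself is slightly shorter.

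**3. How does Cohort 1 compare?**

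| | Cohort 1, Visit 2 | Cohort 2, Visit 1 |
|---|---|---|
| Dose | "Administration of 10 boluses of kisspeptin 0.313 µg/kg IV every hour beginning at hour 1 of the study" | "Option 2: Kisspeptin 0.313 µg/kg IV q 90 minutes will be administered using a closed IV system", or Option 1: SC, 0.313-13.19 µg/kg, q60-q240 min |
| BP and temperature criteria | BP >180/105, temperature ≥101.5°F | Same |
| Readings tied to kisspeptin | Every 10 min, for up to 30 min | None |

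The bolus is identical only for Option 2. The Cohort 1 limit of 30 minutes is a ceiling, so readings at 10, 20 and 30 minutes are the most that it implies, not a guaranteed three.

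**4. Do Visits 2-7 have the same gap?** No. By then dosing is under way, so every set follows earlier boluses. If dosing is on schedule, a set falls within one dosing interval of a bolus: at most 90 minutes for Option 2, and 60 to 240 minutes for Option 1 depending on the interval chosen.

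**5. What does a Visit 1 fix add?**

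- Current minimum over Visits 1-7: 7 × 1 = 7 sets.
- With the fix, Visit 1: 1 pre-dose + 1 to 3 post-dose = 2 to 4 sets.
- With the fix, Visits 2-7: 6 × 1 = 6 sets, unchanged.
- New minimum: 8 to 10 sets. Extra: 1 to 3 per participant, and 5 × (1 to 3) = 5 to 15 for N=5.

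**6. What does the fix leave open?** If the last Visit 1 reading is 30 minutes after a bolus given near the start of sampling, the interval to Visit 2 is still about 21 − 0.5 = 20.5 h to 27 − 0.5 = 26.5 h.

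**The case against.** The best defence is that the rule is a floor. It permits a pre-dose-only set but does not direct one. A study physician starts dosing, and staff are drawing blood over the next 80 minutes. Entry requires blood pressure below 140/90, well under the termination limits, and a past medication reaction needing emergency care is an exclusion. The Justification of doses section calls the IV dose physiologic in healthy adults. Recognising an allergic reaction does not depend on a scheduled set of vital signs. All of this stands and keeps the point minor. It does not supply a blood pressure or temperature reading, because staff presence is not a required measurement.

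The comparison with Cohort 1 is also open to challenge. Cohort 1 has 12-hour admissions, ten hourly boluses given by a nurse, larger blood volumes and a GnRH bolus, and the documents give no rationale for either schedule. That stands too: the difference cannot be called an oversight. The comparison shows only that the protocol already has a workable rule tied to kisspeptin.

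A reader might infer three stronger points, none of which the documents support:

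- **That Visits 2-7 need retiming.** Those sets already follow earlier boluses, and no benefit of moving them is shown.
- **That a day-long unmonitored period is the defect, and that the fix cures it.** Dosing continues between outpatient visits under any version of the Visit 1 rule, and nearly all of that interval stays without a required reading.
- **That the SC range makes Cohort 2 riskier.** The top SC dose is 13.19 / 0.313 = about 42 times the Cohort 1 bolus in µg/kg, but the routes differ, so this is not an exposure ratio.

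**Conclusion.** The point holds for Cohort 2 Visit 1 only. The number of blood pressure and temperature readings guaranteed between the first Cohort 2 dose and Visit 2 is zero. If the Visit 1 set is taken before dosing, the next required reading comes roughly a day later. The length of that interval rests on Visit 2 falling on the next calendar day and on when during Visit 2 the set is taken.

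The documents identify no blood pressure or temperature hazard from kisspeptin, and no size of risk is claimed. The point rests on the termination criteria needing readings that the schedule does not secure at the first dose. It is worth considering as a safety improvement.

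**What to change.** In Cohort 2 Protocol, Visit 1, and in Cohort 2 daily blood sampling visits, require one set of vital signs before the first bolus and at least one set after it, within the existing 80-minute sampling period. Cohort 1's pattern, every 10 minutes for up to 30 minutes, is a ready model. For SC dosing that timing is an assumption, because the documents give no SC time course; the investigators may prefer a later reading within the 80 minutes.

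Leave Visits 2-7, the doses, the visit schedule and the termination limits as they are.

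The cost is a wording change and the extra Visit 1 recordings counted above. They are taken while staff are already drawing blood, so no visit is added. A site that already takes more than one set at Visit 1 would add fewer.

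### Does the Cohort 1 power calculation enter the expected Visit 2 pulse count where the change from Visit 1 belongs?

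*Combined protocol and SAP*

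**What the plan says.** The calculation is in the combined protocol and SAP, under BIOSTATISTICAL ANALYSIS, Cohort 1 (Specific Aim 1), Population Size. The design is paired: "Each patient will serve as her own control". The primary outcome compares the number of LH pulses at the first assessment, without kisspeptin, with the number at the second, with kisspeptin.

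The planning figures follow in this order:

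- Baseline, from one cited study with 10-minute sampling: "approximately 2.25 pulses / 12 h in hyperprolactinemic individuals".
- Expected effect of treatment: "During the second admission, by administering 10 boluses of kisspeptin, 10 LH pulses should be observed".
- Reduced planning figure and its reason: "8 pulses will be conservatively estimated because some of those pulses will coincide with/conceal endogenous pulses".
- Sample size: "For a difference of 8 and an SD of 6.8, 10 subjects will need to be studied before and after kisspeptin", for 90% power at alpha 0.05.

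The paragraph does not label the 8 as a Visit 2 total or as a net increase. It shows no explicit subtraction of 2.25.

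**The concern.** Read quickly, the sentences seem to track one quantity. Ten pulses are expected at the second admission, the 10 is replaced by 8, and the 8 then appears as the difference. If the 10 is the Visit 2 count, the 8 seems to be one too. The paired difference should then be 8 - 2.25 = 5.75. A check that seems to confirm this is that a net gain of 8 over 2.25 implies 10.25 pulses at Visit 2, more than the 10 the plan expects.

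The stakes would be real. This paragraph is the only justification for 10 women in Cohort 1, and it concerns the primary outcome. At 66% power the trial would miss its own assumed effect about one time in three, while being described as 90% powered.

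**Working it through.** **Inputs** (all from Population Size, Cohort 1): baseline 2.25 pulses per 12 h; 10 boluses expected to give 10 pulses; planning difference 8; SD 6.8; n = 10; power 90%; alpha 0.05. The plan names neither the test nor its sidedness, and does not say which SD the 6.8 is. I assume a two-sided paired t-test with 6.8 as the SD of the within-woman differences.

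**Formula.** Noncentrality = (difference / SD) × √n, with n - 1 = 9 degrees of freedom. Power comes from the noncentral t distribution.

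**Step 1: the plan's own figure.** 8 / 6.8 × √10 = 3.72, power 91.0%. The smallest n that reaches 90% is 10, so the figure reproduces. Other methods do not return 10:

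| Method at difference 8 | n for 90% power |
|---|---|
| Paired t, two-sided, SD of differences 6.8 | 10 |
| Paired t, one-sided | 8 |
| Normal approximation, two-sided | 8 |
| 6.8 as per-visit SD, zero correlation (6.8 × √2 = 9.62), two-sided | 18 |
| Two independent groups | 16 per group |

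Of these, only the two-sided paired t-test on differences gives 10, which supports the assumption above.

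**Step 2: what overlap does to the counts.** Suppose all 10 boluses respond and endogenous pulses continue at the baseline rate. Let k be the number of endogenous pulses that coincide with, or are hidden by, induced pulses, so k runs from 0 to 2.25.

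- Visit 2 total = 10 + 2.25 - k
- Difference = (10 + 2.25 - k) - 2.25 = 10 - k

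The Visit 2 total then lies between 10 and 12.25. A merged pulse is still counted once, so overlap alone can never give a total of 8. The difference lies between 7.75 and 10. At k = 2 the Visit 2 total is 10.25 and the difference is exactly 8. The baseline cancels inside this expression, so it has already been subtracted.

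**Step 3: power over that range, and under the disputed reading** (n = 10, SD 6.8).

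| Case | Difference | Noncentrality | Power | n for 90% |
|---|---|---|---|---|
| No endogenous pulse concealed | 10 | 4.65 | 98.4% | 8 |
| About 2 concealed (the plan's 8) | 8 | 3.72 | 91.0% | 10 |
| All 2.25 concealed | 7.75 | 3.60 | 89.3% | 11 |
| 8 taken as the Visit 2 total | 5.75 | 2.67 | 66.4% | 17 |

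If all boluses respond, 7.75 is the smallest difference, not the best case. The plan's 8 sits near the bottom of the 7.75 to 10 range, which fits its description as conservative.

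**Step 4: what the last row needs.** A Visit 2 total of 8 requires at least two of the ten boluses to produce no pulse. The plan never says this. The only reason it gives for the reduction is overlap.

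**The case for a change.** The best case for the concern is the word order. The 10 is described as what should be observed at the second admission, the 8 replaces it, and no subtraction is shown. The text never calls the 8 a net gain. If 10 really is the observed total, the difference is 7.75, so 8 is slightly optimistic.

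Part of this stands. The paragraph leaves the reader to work out what the 8 is, and it gives no source or description for the SD of 6.8. Sidedness is also left unsaid. These are gaps in explanation, and they do not show that the calculation is wrong.

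The rest does not stand. The plan ties the 10 pulses to the 10 boluses, and the next sentence presumes that endogenous pulses also occur at Visit 2. Ten is therefore not a ceiling on the Visit 2 total, and 10.25 contradicts nothing. The Cohort 1 Protocol also places a GnRH bolus at hour 11 of the same 12-hour sampling, another reason not to treat 10 as a cap. If 7.75 is preferred to 8, power moves from 91.0% to 89.3% and the sample size from 10 to 11, which is within the roundness of the planning figures.

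The feared over-reading of a null result has no hook in the plan either. Data Analysis and Interpretation says when the hypothesis will be accepted and gives no rule that treats a null result as evidence of no effect.

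**Conclusion.** The concern does not hold. The plan's reason for going from 10 to 8 makes sense only if 8 is the gain over baseline, and that is how the next sentence uses it: "For a difference of 8 and an SD of 6.8". On that reading the stated 90% power with 10 women reproduces at 91.0%, and it stays at 89.3% or above over the range that overlap alone can produce. The 66% figure arises only if 8 is a Visit 2 total, which the stated reason cannot yield. Writing 8 - 2.25 into the plan would count the baseline twice and replace a figure that reproduces.

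This rests on four assumptions: every bolus induces a pulse, as the plan expects; endogenous pulses at Visit 2 occur at the 2.25 baseline rate; the test is a two-sided paired t-test; and 6.8 is the SD of the within-woman differences. The last two are not stated, but they match the plan's N exactly. Whether 6.8 is a good value cannot be judged from the documents, and that is a separate question from the one raised here.
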